### 3.k Safety Reporting

The Principal Investigator (PI) and study staff members are responsible for the safety of study participants. It is not anticipated that there will be any significant physical or psychological risks associated with this study. However, federal regulations require prompt reporting to the University of North Carolina at Chapel Hill Institutional Review Board (IRB), all injuries, adverse events, or other unanticipated problems involving risks to subjects or others that occur in the course of a subject's participation in this research study.

Study team members who become aware of any adverse event related to the study will notify the principal investigator, [name], immediately. Study team members will have contact information for [name] for daytime, evening and weekend hours. If [name] is not available for contact when a study team member becomes aware of a study-related adverse event, [name], Medical Monitor on the study, will be contacted. Once [name] or [name] are contacted about the adverse event, he will make a determination about the reporting requirements in accordance with the University of North Carolina at Chapel Hill IRB guidelines. This will include notification of the University of North Carolina at Chapel Hill IRB within one week for a serious adverse event, and within 2 weeks business days if a protocol deviation/violation, or other unanticipated problem.

The Principal Investigator will report all adverse events and protocol deviations to the safety officer, [name], on a biannual basis, or as requested. The PI or co-investigator will report all serious adverse events to the

study's safety officer within 48 hours of being made known to the investigator. This immediate report will be followed by a detailed written report as soon as possible.

All adverse events will be collected, analyzed, and monitored in the study's adverse event log, which is kept in the Investigator's regulatory files within a locked file cabinet.

### Definitions

- **Adverse Event (AE)** - An adverse event is any unfavorable and unintended diagnosis, sign (including an abnormal laboratory finding), symptom, or disease temporarily associated with the study intervention, which may or may not be related to the intervention. AEs include any new events not present during the pre-intervention period or events that were present during the pre-intervention period, which increased in severity.
- **Serious Adverse Event (SAE)** – A serious adverse event is any untoward medical occurrence that results in death, is life-threatening, requires or prolongs hospitalization, causes persistent or significant disability/incapacity, results in congenital anomalies/birth defects, or, in the opinion of the investigators, represents other significant hazards or potentially serious harm to research participants or others.

### **3.k.1 Adverse Event Reporting**

All AEs are collected, analyzed, and monitored by using an Adverse Event Form, a sample of which is shown in **Appendix B**. AEs and/or laboratory abnormalities identified in the protocol as critical to participant safety will be reported to the NIAMS, the independent safety officer ([name]) and the . All AEs experienced by the participant during the time frame specified in the protocol (e.g., from the screening visit until the 8 week follow-up) will be reported, as outlined in the protocol.

### **3.k.2 Unanticipated Problems**

Unanticipated Problems are not included in the 45 CFR part 46, but are defined by the OHRP as any incident, experience or outcome that meets all of the following requirements:

- (1) Unexpected (in terms of nature, severity, or frequency) given (a) the research procedures that are described in the IRB-approved research protocol and informed consent document; and (b) the characteristics of the participant population being studied;
- (2) Related or possibly related to participation in the research. *Possibly related* means there is a reasonable possibility that the incident, experience, or outcome may have been caused by the procedures involved in the research); and
- (3) Suggests that the research places participants or others at a greater risk of harm (including physical, psychological, economic, or social harm) than was previously known or recognized.

OHRP recognizes that it may be difficult to determine whether a particular incident, experience, or outcome is unexpected and whether it is related or possibly related to participation in the research. OHRP notes that an incident, experience, or outcome that meets the three criteria above generally will warrant consideration of substantive changes in the research protocol or informed consent process/document or other corrective actions in order to protect the safety, welfare, or rights of participants or others.

Examples of corrective actions or substantive changes that might need to be considered in response to an unanticipated problem include:

- Changes to the research protocol initiated by the investigator prior to obtaining IRB approval to eliminate apparent immediate hazards to subjects;
- modification of inclusion or exclusion criteria to mitigate the newly identified risks;
- implementation of additional procedures for monitoring subjects; suspension of enrollment of new subjects;
- suspension of research procedures in currently enrolled subjects;
- modification of informed consent documents to include a description of newly recognized risks;
- provision of additional information about newly recognized risks to previously enrolled subjects.

Only a small subset of adverse events occurring in human subjects participating in research will meet these three criteria for an unanticipated problem. Furthermore, there are other types of incidents, experiences, and outcomes that occur during the conduct of human subjects research that represent unanticipated problems but are not considered adverse events. For example, some unanticipated problems involve social or economic harm instead of the physical or psychological harm associated with adverse events. In other cases, unanticipated problems place subjects or others at increased risk of harm, but no harm occurs. For further information see <http://www.hhs.gov/ohrp/policy/advevntguid.html>.

### **3.k.3 Serious Adverse Event Reporting**

All serious adverse events (SAEs), unless otherwise specified in the protocol and approved by the IRB and the NIAMS, require expedited reporting by the Principal Investigator ([name]) to the study's safety monitoring officer ([name]). SAEs must be reported to the independent safety monitoring officer and the NIAMS, through the NIAMS contractor within 48 hours of being reported to the Investigator. The immediate reports should be followed by detailed, written reports as soon as possible. Follow up information may be required. All interventional studies, independent of phase or type, must report SAEs.

If a potential SAE is reported to any study personnel that study personnel should make [name] aware of the potential SAE at once. [name] will make [name], the independent safety officer and the Medical Monitor, [name], aware of the nature of the SAE by phone in the first 24 hours of the SAE being reported to the study personnel. [name] will personally collect information from healthcare professionals involved in the study, the study participant and close relatives (if possible), and other study personnel. [name] will provide written documentation to the 1) independent safety officer ([name]), 2) NIAMS and 3) the Institutional Review Board at the University of North Carolina at Chapel Hill within 48 hours of learning about the SAE. A single form (**Appendix B**) will be completed and sent to all three people/institutions by electronic mail with signatures of the Principal Investigator, [name], and the Medical Monitor, [name]. The action regarding the treatment of that specific patient taken by [name] and [name] will be indicated on the form (Dose decreased, Dose increased, Dose delayed, Discontinued permanently, Discontinued temporarily, Other), as well as actions that are taken for the study in general (No action, Modification of consent documents to include a description of newly recognized risks, Revise protocol to eliminate apparent immediate hazards to subjects, Notify currently enrolled subjects, Suspension of enrollment of new subjects, other). The safety officer, IRB and NIAMS will be asked to notify [name] if they disagree with the specific actions taken within 72 hours.

If the safety officer, IRB and NIAMS disagree with actions taken by [name] and [name] regarding a specific SAE a conference all between aforementioned personnel and institutes will be scheduled with 72 hours of [name] being notified of the disagreement. Study recruitment will be halted until the conference call has occurred and an agreement is conferred among all personnel and institutional representatives about stipulations regarding reopening study recruitment.

### **3.1 Data and Safety Officer**

The principal investigator will oversee data collection monitoring and all issues related to participant safety, data collection protocols, and participant confidentiality. All adverse events will be collected by physical therapists supervising the therapeutic resistance exercise and any study-related issues pertaining to safety or adverse events will be reported to the TARC Methodology Core, which works directly with the Regulatory Core of the NC TraCS Institute for monitoring adverse events of studies conducted through TARC. [name], Co-Director of the TARC Methodology Core, will be responsible for the decisions and communication with NC TraCS Regulatory Core since she is not a co-investigator or collaborator on this project. [name] has previous experience as a principal investigator in physical therapy based interventions for patients with knee osteoarthritis and therefore has the experience and knowledge regarding the scientific area of study and study design which will be important in understanding the analysis and interpretation of the data to ensure participant safety as well as ethical, scientifically rigorous study conduct. The *conflict of Interest (COI) Statement* forms have been collected from [name] (See **Appendix G**).

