### **3.g Study Intervention**

#### *Intervention Overview*

The current study is a **Phase 1 clinical trial** that will have three randomized groups. All groups will receive the same supervised, standardized TE program at the UNC Meadowmont Physical Therapy Clinic. *TENS+TE* and *sham TENS+TE* patients will be instructed to utilize their device during all 12 physical therapy sessions as well as 8 hours per day when they are the most active for 4-weeks (28 days). Twelve TE sessions over 4 weeks is the current standard of care for patients with knee OA at the UNC Meadowmont Physical Therapy Clinic. Additionally, previous data indicate strong effect sizes for neuromuscular improvements following a 12 session/4-week intervention. Patients included in this study will be treated by 1 of 4 physical therapists (PT) associated with this study during each session (see participating physical therapists listed below). Patients in all groups will receive TE for their involved leg 3 times per week for 4 weeks (12 sessions). The PTs will review each patient's medical history and physician instructions before starting TE. A PT will conduct a lower extremity physical assessment prior to beginning rehabilitation and following the 4-week intervention for clinical use. *The overall goals of the TE program are to increase lower extremity strength and function.* Progressive exercise will be similar to that previously reported by the PI. Procedural reliability of the intervention will be maximized using: 1) training sessions for the PTs to ensure all exercises are taught and progressed in the same manner, 2) tracking compliance of *TENS/ sham TENS+TE*, 3) biweekly review patient charts regarding exercises, and 4) biweekly evaluation of therapeutic exercise delivery on a subset of patients at random time points using a rubric. Lower extremity strengthening will be progressed through open and closed chain strengthening (see exercises in tables X-X). Range of motion limitations and soreness will be addressed or managed with stretching, manual therapy, and/or cryotherapy. All strengthening exercises will be systematically progressed, on an individual basis, using the daily adjustable progressive resistive exercise system. Functional exercises will be progressed according to the patients' ability and any reactive inflammation from TE.

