## *Baseline Assessment*

Five questionnaires will be completed during the baseline assessment, which occurs within 7 days prior to the initiation of the intervention and includes 1) the Physical Activity Scale for the Elderly (PASE), 2) Self-Efficacy for Physical Activity (SEPA), 3) the Short Form 12 (SF-12), 4) the Charlson Morbidity Index, and 5) Visual Analog Scales (VAS) to determine the likelihood to continue current level of physical activity, current level of knee pain, and tolerability of walking.

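### All adverse events are assigned to the physical therapists, whose contact spans about half of the screening-to-week-8 window; elsewhere the visible text provides only passive capture

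*Combined protocol and SAP*

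**What the plan says.** Section 3.1 (Data and Safety Officer) names one group as collector: "All adverse events will be collected by physical therapists supervising the therapeutic resistance exercise".

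Section 3.g (Intervention Overview) fixes when those therapists see patients: "Patients in all groups will receive TE for their involved leg 3 times per week for 4 weeks (12 sessions". It adds one contact at each end: "A PT will conduct a lower extremity physical assessment prior to beginning rehabilitation and following the 4-week intervention for clinical use".

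Section 3.k.1 says that all adverse events in the protocol's time frame will be reported, and gives as an example of that time frame "from the screening visit until the 8 week follow-up". It says an Adverse Event Form is used, but not who completes it or at which contacts.

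Two other routes are described. Section 3.k binds "Study team members who become aware of any adverse event related to the study" to notify the principal investigator. Section 3.k.3 has any study personnel who are told of a potential serious event pass it on at once.

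The definitions under section 3.k count events regardless of relatedness, but measure them against the pre-intervention period. The glossary ties them instead to involvement in the research.

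**The concern.** The group assigned to collect every event is in scheduled contact with patients for only part of the period over which events are to be reported. If section 3.1 is followed as written, nobody is assigned to ask about events at screening, at baseline or in weeks 5 to 8, or to ask patients who stop coming to exercise.

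Three kinds of event are exposed: those following the laboratory screening tests, which include a burst superimposition test before any therapist contact (section 3.e.1); non-serious events in the four weeks after treatment; and events in patients who leave the exercise programme, possibly because of the event. The trial is labelled Phase 1, and adverse events go into the biannual safety reports (section 3.m.1). Under-capture would make the safety record look cleaner than it is.

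**Working it through.** The plan states no coverage figure, so there is none to reproduce. The check has two parts.

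**Share of the window with scheduled therapist contact**

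Inputs:
- Therapist period: 4 weeks (Intervention Overview), 4 × 7 = 28 days.
- Follow-up 2: 8 weeks (section 3.i.1), 8 × 7 = 56 days. Assumption: counted from the start of treatment.
- Baseline lead-in: at most 7 days (section 3.n.1, Baseline Assessment).
- Screening-to-baseline interval: not given.

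Formula: share = therapist days / window days.
- From treatment start: 28 / 56 = 50%.
- With the full lead-in: 28 / (56 + 7) = 28 / 63 = 44%.
- If screening comes before baseline, the share is lower by an amount the documents do not allow one to compute.

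Days without scheduled therapist contact are therefore about 56 − 28 = 28 after treatment, plus 0 to 7 or more before it. The figures are approximate because the two therapist assessments are not dated. They extend contact slightly at each end, but not to screening or through weeks 5 to 8.

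**What covers the remaining time**

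| Period | Therapist | Other staff contact | Listed forms that ask about adverse events |
|---|---|---|---|
| Screening | None | Laboratory visit | None among the three forms |
| Baseline | None at the laboratory visit | Laboratory visit | None among the five questionnaires |
| Weeks 1 to 4 | 12 sessions | Weekly call and meeting | None; medication log and scales for tolerability, satisfaction and keeping appointments |
| 4-week visit | Clinical assessment after the intervention | Laboratory visit | None among the five questionnaires |
| Weeks 5 to 8 | None | No calls scheduled | None |
| 8-week visit | None | Laboratory visit | None among the six questionnaires |

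Forms are as listed in section 3.n.1. The weekly calls and meetings (section 3.d.1) belong to the intervention weeks and deal with questions, concerns and satisfaction. The five administrative forms in section 3.n.4 include no adverse event form.

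The section 3.k and 3.k.3 routes have no time limit, so they apply throughout. Both start only when information happens to reach staff. The first is limited to events related to the study, the second to potential serious events. A non-serious event in week 6 that nobody connects with the study meets the section 3.k definition and falls in the section 3.k.1 window, yet has no assigned collector.

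The start of the window is also unsettled. Section 3.k.1 starts its example at screening, whereas the section 3.k definition counts what is new or worse than the pre-intervention period. An event between screening and first treatment is in the window under one and may not be an event under the other.

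**The case against.** A reader might infer that the window outside the exercise weeks is simply not covered. The text does not support that. Staff must pass on study-related events and potential serious events whenever they learn of them. There is an adverse event log, all events go to the safety officer biannually, and closeout requires every event to be recorded and followed to resolution. Staff see patients at 4 and 8 weeks. These provisions govern what happens once an event is known; they do not assign anyone to ask.

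A reader might set 12 × 45 minutes of exercise against device use planned for "8 hours per day when they are the most active for 4-weeks" and infer that almost all exposure goes unobserved. That ratio does not measure coverage. Events are found by asking, and all 28 device days fall within the therapist period, so an event at home can be reported at the next session.

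A reader might also infer bias between arms. The exercise contact is planned identically in all three. Device patients receive telephone numbers for unblinded staff and no such channel is described for exercise alone, so unequal volunteering is conceivable, but nothing shows it.

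For patients who stop attending, weekly calls continue to be planned during the intervention and reasons for drop-out are collected (section 3.i.2). This helps in part, but neither is an adverse event enquiry.

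The form lists are imperfect evidence. The 4- and 8-week lists are evidently carried over from the baseline text and omit the WOMAC, which is an outcome. Appendices E (visits and evaluations) and F (adverse event forms) are named but not in the text, and the window is an example that defers to a protocol in Appendix A. An enquiry there cannot be excluded. If one exists, section 3.1 still assigns all collection elsewhere and needs correcting.

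Finally, the device is cleared for arthritis pain, the plan anticipates no significant risk, and no comparison of event rates is visible. That limits the consequences but does not remove the gap in the safety record.

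**Conclusion.** The point stands as a gap in assigned, active collection. The only named collector of all adverse events has scheduled contact for about 50% of the time from treatment start to week 8, or 44% with the full baseline lead-in. Outside that period, capture in the visible text is passive and limited to study-related or serious events, although the plan's own definition includes unrelated ones. Non-serious events after screening tests, in weeks 5 to 8, or in patients who stop attending are likely to be under-captured. The documents give no basis for estimating how many.

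This rests on week 8 being counted from treatment start, and on the unseen appendices not containing a scheduled enquiry. The change should be made: it is cheap and uses contacts and a form that already exist.

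**What to change.** Amend section 3.1 so that, in all three arms, study staff ask one scripted open question about adverse events and complete the existing Adverse Event Form:

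- at the baseline visit;
- in each weekly call already planned during the intervention;
- at the 4-week and 8-week visits.

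This should include patients who have stopped exercise. The 8-week question matters most for the post-treatment period, because the weekly calls do not extend into it. Therapists continue to report what they see. List the form in the matching packets in section 3.n.1.

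At laboratory visits an existing team member other than the blinded outcome assessor should ask. Sections 3.c and 3.h give follow-up testing to blinded investigators, and a complaint about the device could reveal allocation.

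Reconcile sections 3.k, its definitions, 3.k.1 and 3.1 on two matters: when the window starts, and whether events judged unrelated are collected.

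The cost is about a minute per contact, a line in each packet, more minor events to log, and the need to keep the answers from the blinded assessors.

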### **3.n Data Collection and Study Forms**

#### **3.n.1 Source Documentation**

All data will be recorded on paper using black ink. All study forms will be printed prior to the beginning of the study and will be organized into participant binders which will contain all study documents necessary to collect each piece of data throughout the entirety of the study. All forms will be distributed to the study participant by either the Principal Investigator, Study Coordinator, or Research Assistant. The member of the study team will describe each of the questionnaires to the study participant, and will read allowed the instructions. The study participant will be allowed to ask any questions about the study questionnaires.

Each study participant will have one complete binder of study forms which consists of consent forms, case report forms, and all questionnaires to be completed by study participants. Each binder will contain packets of study forms, which correspond to the data needing to be collected during the following times throughout the course of the study: 1) initial screening, 2) baseline assessment 3) duration of the intervention, 4) 4-week follow up assessment and 5) 8-week follow up assessment. The study forms contained in each packet are individually described below.

All binders of study forms will be maintained in a locked file cabinet located within the Neuromuscular Research Laboratory. The Neuromuscular Research Laboratory is secured through UNC ID Card swipe access. The Principal Investigator, Study Coordinator, and Research Assistant are the only individuals who will have access to the file cabinet in which the participant binders are stored.

